PROTOCOL

The VITDALIZE Study

Effect of high-dose vitamin D3 on 28-day mortality in adult critically ill patients with severe vitamin D deficiency: a multicenter, placebo-controlled double-blind phase III RCT

EudraCT number 2016-002460-13

PRINCIPAL INVESTIGATOR

[name], MSc, Associate Professor
Medical University of Graz
Department of Internal Medicine
Division of Endocrinology and Diabetology
[name]
[name]
Austria
[contact]
[contact]

Medical University of Graz

SYNOPSIS

STUDY NAME	The VITDALIZE Study: Effect of high-dose vitamin D3 on 28-day mortality in adult critically ill patients with severe vitamin D deficiency: a multicenter, placebo-controlled double-blind phase III RCT
SPONSOR	Medical University of Graz [name] [name], Austria
STEERING COMMITTEE	Consists of the coordinating investigator and co-investigators
EARLIEST START DATE	Q2 2017
RECRUITMENT PHASE	2-3 years
FOLLOW UP	12 months
STUDY CENTER	Ca. 30 (ca. 15 non-academic)
PARTICIPATING COUNTRIES	Austria Germany Switzerland/UK/Belgium
RATIONALE & BACKGROUND	In the VITdAL-ICU trial using a large oral dose of vitamin D3 in 480 adult critically ill patients, there was no benefit regarding the primary endpoint hospital length of stay. However, the predefined subgroup with severe vitamin D deficiency (25(OH)D ≤ 12ng/ml) had significantly lower 28-day mortality (36.3% placebo vs. 20.4% vitamin D group, HR 0.52 (0.30-0.89), number needed to treat = 6). Therefore, high-dose vitamin D3 in a population of severely vitamin D deficient critically ill patients is a promising and inexpensive intervention that requires confirmatory multicenter studies. To date, only 7 interventions (e.g. noninvasive ventilation or prone positioning) have ever demonstrated mortality benefit for ICU patients in multicenter trials. In case of benefit, vitamin D treatment in critically ill patients could be immediately implemented worldwide.
TARGET NUMBER OF PATIENTS TO BE INCLUDED	Maximum 2400 patients (1200 per group) 1 interim analysis after 1200 patients

	The sample size is based on an anticipated 5% absolute mortality reduction assuming an overall 28-mortality of 25% in the placebo group
INTERVENTION	Cholecalciferol (vitamin D3) versus placebo: Day 0: One single bolus loading dose 540,000 IU of oral (or enteral) vitamin D3 followed by 4000 IU of vitamin D3 daily for the entire active study period (90 days) versus placebo (medium chain triglycerides, MCT) – total dose 900,000 IU vitamin D3

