If the major inclusion criterion of severe vitamin D deficiency is met, the other inclusion and exclusion criteria are evaluated by the local investigator/s at Visit 1. Informed consent will be ascertained whenever possible.

BASELINE ASSESSMENTS

- Age
- Sex
- ICU admission diagnosis
- ICU type
- Charlson comorbidity index
- SAPS III
- TISS 28
- 25(OH)D routine testing
- qSOFA
- Katz Activities of daily life

At baseline, data on demographic and clinical characteristics of the patients are obtained. At Centers of Medical University Graz it is planned to take a blood sample before the loading dose on day 0 and day 5 to ascertain biochemical response. The samples will be stored frozen at -70 C until batch analysis. In this subgroup (Medical University Graz), also stool samples will be collected for microbiome analysis on day 0 and day 5 . Stool samples are stored at -80°C

The Charlson comorbidity index, SAPS III and TISS 28 will be determined to be able to adjust for severity of illness and preexisting comorbidities.

RANDOMIZATION AND BLINDING

Patients will be randomly assigned to either placebo or vitamin D3 in a 1:1 ratio, using the web-based randomization service "Randomizer for Clinical Trials" developed at the Institute for Medical Informatics, Statistics and Documentation, Medical University of Graz. Patients will be stratified according to trial site (ICU) and gender. An independent statistician will set up the study in the Randomizer.

The following method will be used to maintain the blind: the randomization list from the randomizer.at will be kept strictly confidential and no routine vitamin D testing is done after study inclusion. The independent statistician and unblinded pharmacist will keep treatment allocation information confidential until database lock.

In case of safety concerns (eg. severe hypercalcemia > 3.5 mmol/L), participants of the study may be unblinded by the local investigator at each participating site and/or the coordinating center. This will be done and documented with the Randomizer.

VISIT 1

Study medication

The day of the study medication loading dose is day 0. This is also the start for the calculation of the time dependent outcome data.

VISIT 2 (DAY 5 ±2)

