All clinical and safety data collected in the study will be analysed with SAS v9.4 procedures in a Windows XP environment. Data will be presented as summary tables and, where appropriate, as plots. Continuous data will be described by means, standard deviations, medians and upper and lower quartiles unless otherwise stated. The number of observations and minimum and maximum values are also included. All descriptive summaries will be displayed to one more decimal place than actually measured. Categorical data will be summarized using frequencies and percentages.

Demographic and Baseline Characteristics

In a summary of demographic, baseline and diagnostic characteristics (age, weight, height, sex, SAPS III, Charlson comorbidity index, qSOFA - criteria, laboratory parameters,...) a comparison of the treatment groups will take place. To this end, appropriate descriptive and inferential statistics will be applied. Relevant medical history will be also displayed using summary statistics according to the two treatment groups.

Analysis of primary outcome

The primary outcome will be 28-day mortality defined as time from application of the study medication loading dose (day 0) to day 28 or death. Kaplan Meier estimates of survival curves in each treatment arm will be displayed. Group comparison will be made using a two-sided log rank test. Additionally, a hazard ratio with a 95% confidence interval will be computed from an univariate Cox-proportional hazards regression. Furthermore sensitivity analyses using multivariable Cox-proportional hazards regression will be performed adjusting for important clinical parameters. Details will be defined in the SAP.

Analysis of secondary outcomes

ICU, hospital mortality, 90-day mortality and 1-year mortality will be analysed as the primary outcome. ICU and hospital length of stay are defined as time between application of the study medication (day 0) and discharge at the primary ICU/hospital; readmissions and stays

at other hospitals will not be added, date and hour will be recorded, in case of a missing hour, the time 12am will be used.

At day 5 the SOFA Score is recorded. Organ failures (> 2 SOFA points in each of the 6 categories) will be reported in total and for each organ system separately. To compare the laboratory parameters 25(OH)D and 1,25(OH)₂D levels ANCOVA will be used.

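### Adjusting the primary mortality analysis for the SAPS III score already collected would raise power at the same N; the planned log-rank test is valid but leaves that gain unused

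*Protocol*

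**What the plan says.** Under Analysis of primary outcome the protocol states: "Group comparison will be made using a two-sided log rank test". No strata are named. It adds that "a hazard ratio with a 95% confidence interval will be computed from an univariate Cox-proportional hazards regression". Covariates enter only afterwards: "sensitivity analyses using multivariable Cox-proportional hazards regression will be performed adjusting for important clinical parameters", with details deferred to the SAP.

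Under Randomization and Blinding: "Patients will be stratified according to trial site (ICU) and gender". Under Baseline Assessments: "The Charlson comorbidity index, SAPS III and TISS 28 will be determined to be able to adjust for severity of illness and preexisting comorbidities". The Schedule of Evaluations places all three scores at Visit 1 (day 0).

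The sample size (Sample size considerations) and the stopping rule (Planned interim analysis) both rest on the log-rank test. Missing Data Handling rules out any imputation. Statistical Considerations lets the SAP override the protocol and requires it to be final before the interim lock. The SAP is not available here.

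**The concern.** The design treats ICU, gender and severity of illness as relevant to outcome. Sample size considerations even explains the lower assumed placebo mortality by less severely ill patients at smaller sites. Yet none of these variables enters the analysis that decides the trial.

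When a baseline variable predicts death strongly, a treatment test that conditions on it has more power at the same N. The trial is sized at 80% power for a 5-point difference in mortality. At stake is therefore some avoidable risk of missing an effect of that size, when the data that would reduce the risk are to be collected anyway.

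**Working it through.** **1. The plan's own figures.** Inputs from Sample size considerations: mortality 25% against 20%, two-sided alpha 0.05, power 80%, 1:1 allocation.

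- HR = ln(0.80)/ln(0.75) = 0.7757.
- Freedman events = (1.960 + 0.842)² × ((1 + HR)/(1 − HR))² = 7.849 × (1.7757/0.2243)² ≈ 492. Mean mortality is 0.225, so N = 492/0.225 ≈ 2187 (stated 2186).
- Schoenfeld events = 4 × 7.849/(ln 0.7757)² ≈ 487 (stated 486).
- O'Brien-Fleming-type spending with one look at half the information gives a two-sided interim level of 0.00305 and an inflation factor of 1.0037. Then 2186 × 1.0037 = 2194 patients and 2194 × 0.225 ≈ 494 events, as stated. Power at 494 events is 0.800.

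The plan's numbers therefore reproduce for a log-rank test without strata or covariates.

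**2. Power at the same N with adjustment.** Simulated trials had N=2194, 30 ICUs (the synopsis gives about 30 centres) and randomisation within ICU by sex. Marginal mortality was held at 25% against 20%, and the critical value was 1.96. All four tests were applied to the same simulated data.

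Not in the protocol, and so assumed: the score's AUC, the between-ICU SD of the log hazard, blocks of 4, 35% in one sex category, no effect of sex on mortality, and a constant hazard over 28 days. There were 2000 runs per row at SD 0.3 and 3000 at SD 0.6, with a Monte Carlo error of up to about 0.9 points.

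| ICU SD | Score AUC | Plain log-rank | Log-rank stratified by ICU × sex | Cox + score | Cox + score, stratified |
|---|---|---|---|---|---|
| 0.3 | no score effect | 80.2% | 80.8% | 80.0% | 80.8% |
| 0.3 | 0.65 | 81.1% | 81.0% | 83.7% | 83.9% |
| 0.3 | 0.73 | 81.3% | 81.8% | 86.4% | 87.0% |
| 0.3 | 0.79 | 81.4% | 81.4% | 91.9% | 91.0% |
| 0.6 | no score effect | 80.8% | 82.9% | 80.9% | 82.8% |
| 0.6 | 0.65 | 81.7% | 83.4% | 83.2% | 85.3% |
| 0.6 | 0.72 | 81.5% | 83.0% | 87.3% | 89.9% |

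At SD 0.3 the score adds 2.6, 5.1 and 10.5 points. Stratification alone adds between about 0 and 2 points across the table.

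**3. The gain as information.** The ratio is ((z₁ + 1.96)/(z₀ + 1.96))², where z₁ and z₀ are the normal quantiles of adjusted and unadjusted power. At SD 0.3 it is 1.07, 1.15 and 1.39 for AUC 0.65, 0.73 and 0.79. At AUC 0.73 this is worth about 0.15 × 2194 ≈ 330 patients.

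**4. Type I error.** With no treatment effect, the plain log-rank test rejected in 3.9% to 4.2% of runs, the stratified log-rank in 4.2% to 4.4%, and the adjusted Cox tests in 3.9% to 4.4%. All are valid.

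**5. Effect measure.** With the marginal HR at 0.78, the HR conditional on score and ICU is 0.75 at AUC 0.73 and ICU SD 0.3.

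**The case against.** The strongest reply is that nothing here is wrong. Sample size, interim rule and primary test all use the same log-rank test, the figures reproduce, and the promised 80% is delivered. Adjusted models are planned, and the SAP may refine them. The word unstratified does not appear; it is inferred from a log-rank test with no strata beside a univariate Cox model. The size of the gain depends on an AUC that the protocol does not give. Eligibility excludes imminent death and requires an anticipated stay of at least 48 hours, which may narrow the spread of risk. All of this stands, and it limits the point to efficiency.

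Three stronger readings are tempting, and the protocol does not support them:

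- A reader might infer that nothing says which result counts if the adjusted and unadjusted analyses disagree. The hierarchy is explicit: the log-rank test makes the comparison and governs early stopping, and the multivariable models are labelled sensitivity analyses.
- A reader might infer that ignoring the randomisation strata is a main source of lost power. Unless ICUs differ greatly in mortality, it costs almost nothing. Nearly all the gain comes from the severity score.
- A reader might take the unadjusted HR as biased towards 1. The marginal 0.78 is the quantity on which the trial was sized. The adjusted HR is a different, conditional quantity.

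The reply does not remove the core. The protocol does more than leave a detail open: it fixes a univariate estimate and confines adjustment to sensitivity analyses, after collecting the scores in order to adjust.

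**Conclusion.** The point holds as a worthwhile, inexpensive improvement to a valid analysis. Pre-specified severity adjustment would raise power at N=2194 from about 81% to about 84-92% if the score's AUC lies between 0.65 and 0.79. That range is an assumption, as are the single well-behaved score and the constant hazard. The direction of the gain does not depend on the exact value, but its size does. A log-rank test stratified by ICU and sex would be a weak substitute. Neither the sample size nor the type I error of the planned test is in question.

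**What to change.** Before the SAP is finalised for the interim lock:

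1. Make the primary test the treatment term of a Cox model with SAPS III and sex as covariates, stratified by ICU, at both the interim and the final analysis. Fix a rule for pooling small ICUs in advance: at the interim, 1200 × 0.225 = 270 expected deaths over about 30 ICUs is roughly 9 per ICU.
2. Align Planned interim analysis, which ties stopping to the log-rank p-value. The same threshold would apply to the p-value of the new test.
3. Make an exception in Missing Data Handling for missing baseline SAPS III, for example simple imputation from baseline data only, so that no patient leaves the ITT analysis.
4. State that the adjusted HR is conditional, and so expected to lie further from 1 than the marginal 0.78 used for sizing.
5. Keep the unadjusted log-rank test, the univariate HR and the Kaplan-Meier curves as supportive analyses.

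The cost is SAP text and matching protocol wording in three places (primary analysis, interim rule, missing data). No new data or patients are needed. The protocol does not say how often SAPS III will be missing, so item 3 should not be left out.

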A very limited number of intervention trials, most including less than 30 patients, have been published. The only phase III study, our VITdAL-ICU study recruited from 2010 to 2012 and (n=475) did not find a difference in the primary endpoint „length of hospital stay“ between placebo and high-dose vitamin D3. However, there was a non-significant absolute risk reduction in all-cause hospital mortality in the total population. The difference was larger (17.5%) and significant in the predefined subgroup of patients with severe vitamin D deficiency at baseline, see Kaplan Meier curve below (n=200, 28.6 vs 46.1%, p=0.01, 0.56 (0.35-0.90)), corresponding to a number needed to treat of 6. (51)

As this was only a secondary endpoint in the predefined subgroup with severe vitamin D deficiency, this finding is hypothesis generating and requires further study, leading to this application.

In our study, we were unable to identify a mechanism by which this benefit was achieved. Interestingly, looking at the causes of death, the vitamin D group seemed to benefit in every category (see below).

Table 2. Length of Stay and Mortality Outcomes for the Total and Subgroup Populations

	Total Study Population (N = 475)			Prespecified Subgroup Population					
	Placebo (n = 238)	Vitamin D ₃ (n = 237)	P Value	Severe Vitamin D Deficiency ^a (n = 200)			Less-Severe Vitamin D Deficiency ^b (n = 275)		
				Placebo (n = 102)	Vitamin D ₃ (n = 98)	P Value	Placebo (n = 136)	Vitamin D ₃ (n = 139)	P Value
Length of stay, median (range)									
Hospital, d ^c	19.3 (0.1-154.1)	20.1 (0.2-181)	.98	19.0 (1.0-154.1)	20.1 (0.2-181)	.40	20.5 (0.1-113.9)	20.1 (0.2-133)	.47
ICU, d	10.7 (0.1-154.1)	9.6 (0.2-181)	.38	9.1 (0.8-154.1)	9.7 (0.2-181)	.98	12.3 (0.1-113.9)	9.0 (0.2-127)	.26
Mortality, No. (%)									
ICU	63 (26.5)	54 (22.8)		34 (33.3)	23 (23.5)		29 (21.3)	31 (22.3)	
HR (95% CI)	0.97 (0.67-1.39)		.86	0.70 (0.41-1.19)		.18 ^d	1.32 (0.79-2.20)		.28 ^d
28-d	68 (28.6)	52 (21.9)		37 (36.3)	20 (20.4)		31 (22.8)	32 (23.0)	
HR (95% CI)	0.76 (0.53-1.09)		.14	0.52 (0.30-0.89)		.02 ^d	1.06 (0.64-1.73)		.83 ^d
Hospital	84 (35.3)	67 (28.3)		47 (46.1)	28 (28.6)		37 (27.2)	39 (28.1)	
HR (95% CI)	0.81 (0.58-1.11)		.18	0.56 (0.35-0.90)		.01 ^d	1.12 (0.72-1.77)		.61 ^d
6-mo	102 (42.9)	83 (35.0)		51 (50.0)	34 (34.7)		51 (37.5)	49 (35.3)	
HR (95% CI)	0.78 (0.58-1.04)		.09	0.60 (0.39-0.93)		.02 ^d	0.95 (0.64-1.41)		.81 ^d
Causes of death, No. (%)									

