 - loading dose of 540,000 IU (dissolved in 37.5 ml of medium chain triglycerides - MCT) followed by 4000 IU daily (10 drops) for the entire active study period (90 days)
- Placebo: identical regime – loading dose of 37.5 ml MCT followed by 10 drops daily

This study uses a group sequential design, with one interim analysis when 50% of the planned enrolled patients in each arm (N=600 per arm) have completed their day 28 assessment by the independent data safety monitoring board. The enrollment of patients will continue while the interim analyses is performed.

EARLIEST START DATE

Q2 2017

RECRUITMENT PHASE

Anticipated 2-3 years based on estimated recruitment rates of 20-100 per center and year

END OF STUDY

The end of the study will be reached either at the interim analysis if the data safety monitoring board decides to stop the study prematurely. Otherwise, the study ends when 2400 patients have been included and completed visit 4 (day 90).

COENROLLMENT

Coenrollment may be allowed after careful review of the principal investigators and in case of unlikely biological interference between the VITDALIZE study and another study. This would be the case e.g. for a study assessing transfusion of older versus newer blood products, or different mechanical ventilation strategies. Likely coenrollment will only be executed in the United Kingdom.

OUTCOMES**PRIMARY OUTCOME**

The primary outcome will be 28-day mortality (starting from day 0 when the study medication loading dose is given).

SECONDARY OUTCOMES

Efficacy outcomes

- 90-day mortality
- 1-year mortality
- ICU and hospital mortality
- Hospital and ICU length of stay (starting at day 0, ending at discharge from the trial site or day 90)
- SOFA day 5 (48 hours tolerance)
- Number of organ failures day 5 (0-6; > 2 SOFA points in each of the 6 categories)

20/40

VITDALIZE study protocol, 1.3, 24.01.2018

[figure not shown]
- Laboratory: 25(OH)D and 1,25(OH)2D levels at day 5 (48 hours tolerance)
- Katz Activities of Daily Life (56) at day 90
- Self – reported infections requiring antibiotics until day 90
- Hospital and ICU readmission until day 90
- discharge disposition (home, rehabilitation, other hospital)

Safety outcomes

- Hypercalcemia at day 5 (48 hours tolerance)/during ICU stay
- Self-reported falls, fractures until day 90
- New episodes of kidney stones

PREDEFINED SUBGROUPS

- Kidney function (CKD 4 or lower vs. higher at inclusion)
- Sepsis (admission diagnosis) vs. non sepsis

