Details will be specified in a separate document (SOP Reporting of SAE in intensive care – version June 2016). No separate reporting of rehospitalization or death will be performed because of the expectedly high event rates in the setting of critical illness.

STOPPING RULES FOR THE TRIAL OVERALL

29/40

VITDALIZE study protocol, 1.3, 24.01.2018

A DSMB will monitor trial progress and safety. Should safety concerns evolve, the DSMB might recommend stopping the study at any time. There will be one planned interim analysis for efficacy. In case of overwhelming benefit the DSMB can recommend stopping the trial.

DATA SAFETY MONITORING BOARD (DSMB)

- [name], Prof. em., Critical Care, University Hospital Geneva
- [name], Prof., Department of Geriatrics, University of Zurich
- [name], Department of Statistics, Medical University of Vienna

STATISTICAL CONSIDERATIONS

The statistical analysis here presented will be detailed in a Statistical Analysis Plan (SAP). Should the SAP and this protocol differ, the methods in the SAP prevail. The SAP will be finalized before database lock for the planned interim analysis.

DEFINITION OF ANALYSIS SETS

Study participants who do not provide an informed consent after regaining consciousness and refuse to provide any more information are excluded from the study and will not be included in any statistical analysis.

INTENTION-TO-TREAT POPULATION

The primary analysis will be performed on the intention-to-treat population (ITT). The ITT will include all patients who receive at least the loading dose of the study medication. All patients included here will be analysed according to the treatment assignment during randomisation.

PER PROTOCOL POPULATION

The per protocol population will include all patients who received the loading dose and have a compliance > 80%. Compliance is defined as self reported percentage of doses ingested until day 90. Other major protocol violations may also lead to exclusion of patients from the per protocol population. This will be discussed on an individual basis within the study team.

SAFETY POPULATION

The safety analyses will be based on the treated set, which is defined as all randomized patients who receive at least one dose of trial medication. All patients will be analysed according to the treatment they actually received.

DATA ANALYSIS

General aspects

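### ICU and hospital mortality are given the primary outcome's Kaplan-Meier, log-rank and Cox analysis, although they have no stated horizon and live discharge precludes the event

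*Protocol*

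**What the plan says.** Under Data Analysis, Analysis of primary outcome, the protocol takes "28-day mortality defined as time from application of the study medication loading dose (day 0) to day 28 or death". It then states: "Kaplan Meier estimates of survival curves in each treatment arm will be displayed"; "Group comparison will be made using a two-sided log rank test"; and "a hazard ratio with a 95% confidence interval will be computed from an univariate Cox-proportional hazards regression". Adjusted Cox models are added as sensitivity analyses, with their details left to the SAP.

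Under Analysis of secondary outcomes: "ICU, hospital mortality, 90-day mortality and 1-year mortality will be analysed as the primary outcome".

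Neither section gives a horizon for ICU or hospital mortality, a rule for patients discharged alive, or a competing-risks method. Vital status is collected at days 28 and 90 and at month 12 (Schedule of Evaluations; Visits 3 to 5), so the fixed-date mortality outcomes are followed beyond discharge. Hospital and ICU length of stay are secondary outcomes in their own right, observed to discharge or day 90. Under Statistical Considerations: "Should the SAP and this protocol differ, the methods in the SAP prevail".

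**The concern.** The sentence groups four outcomes that are not alike. Death by day 90 or by 1 year can be observed in or out of hospital, and follow-up runs to a fixed date. Death in the ICU or hospital can happen only before discharge.

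If live discharge is treated as censoring, Kaplan-Meier assumes that discharged patients would have gone on dying at the rate of those still in the unit. They are the recovering patients, so the curve overstates the proportion who die there. The log-rank test and the hazard ratio then compare death rates per day of stay, which is a different question from whether fewer patients die in the ICU or hospital.

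At stake is the reading of two listed secondary efficacy outcomes. The protocol plans to test secondary outcomes at 0.05 and to repeat them in the predefined subgroups. Because length of stay is also studied, a difference in discharge rates is something the trial itself allows for.

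**Working it through.** **Figure not affected.** The sample size rests on 28-day mortality and reproduces. The hazard ratio is ln(0.80)/ln(0.75) = 0.776. The Schoenfeld formula gives 487 events (protocol 486), and the two-proportion formula gives 1094 per group (protocol 1093).

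**Step 1: size of the Kaplan-Meier error.** Inputs are from the protocol's Table 2 of the earlier trial, placebo, severe deficiency: ICU deaths 34/102 = 33.3%, median ICU stay 9.1 days; hospital deaths 47/102 = 46.1%, median hospital stay 19.0 days. Assumptions: constant hazards; the median is the time to death or discharge, whichever comes first; live discharge is censored.

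- Total exit hazard: λ = ln 2/median. Death hazard: pλ.
- One minus Kaplan-Meier at t: 1 − exp(−pλt).
- Cumulative incidence at t: p[1 − exp(−λt)].

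ICU: λ = 0.693/9.1 = 0.0762; pλ = 0.0254.
- Day 28: 1 − exp(−0.711) = 51%, against 0.333 × (1 − exp(−2.13)) = 29%.
- Day 90: 1 − exp(−2.285) = 90%, against 33%.

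Hospital: λ = 0.693/19.0 = 0.0365; pλ = 0.0168.
- Day 28: 37.5%, against 29.5%.
- Day 90: 78%, against 44%.

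This error sits within each arm's curve, so it remains when the arms have equal stays.

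**Step 2: size of the hazard-ratio effect.** Under the same model the discharge-censored hazard ratio is (p₁/p₀) × (median₀/median₁). With equal mortality and the less-severe subgroup's ICU medians, it is 12.3/9.0 = 1.37.

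A simulation (1200 per arm, 1000 runs, 90 days, 22% ICU mortality in both arms, those medians) gave:
- censored at discharge: hazard ratio 1.38, rejection in 95% of runs;
- discharged patients kept in the risk set to day 90: hazard ratio 1.03, rejection in 6%.

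With equal discharge hazards in the two arms and a lower death hazard on treatment, the two approaches nearly agree: 0.80 and 0.82 (ICU), 0.78 and 0.80 (hospital).

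**Step 3: the earlier trial's table.** With p the placebo and q the vitamin D proportion, the implied hazard ratio is ln(1−q)/ln(1−p), computed from the counts.

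| Outcome, group | Placebo | Vitamin D | Risk ratio | Implied HR | Reported HR |
|---|---|---|---|---|---|
| ICU, total | 63/238 | 54/237 | 0.86 | 0.84 | 0.97 |
| ICU, severe | 34/102 | 23/98 | 0.70 | 0.66 | 0.70 |
| ICU, less severe | 29/136 | 31/139 | 1.05 | 1.05 | 1.32 |
| Hospital, total | 84/238 | 67/237 | 0.80 | 0.76 | 0.81 |
| Hospital, severe | 47/102 | 28/98 | 0.62 | 0.54 | 0.56 |
| Hospital, less severe | 37/136 | 39/139 | 1.03 | 1.04 | 1.12 |
| 28-day, total | 68/238 | 52/237 | 0.77 | 0.74 | 0.76 |
| 28-day, severe | 37/102 | 20/98 | 0.56 | 0.51 | 0.52 |
| 28-day, less severe | 31/136 | 32/139 | 1.01 | 1.01 | 1.06 |

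The 28-day hazard ratios lie within 0.05 of the values implied by their proportions. The ICU hazard ratios depart most in the less-severe subgroup, where the median ICU stays differ most (12.3 and 9.0 days), and little in the severe subgroup (9.1 and 9.7 days).

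**The case against.** The strongest reply is that the protocol never says discharged patients are censored at discharge. Vital status is known to day 90 and beyond, so they could stay in the risk set to a common horizon, and Step 2 shows that the hazard ratio would then be close to 1 in the equal-mortality case. This stands: censoring at discharge is the usual reading of the instruction, not a written rule.

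A reader might infer that the planned hazard ratios are wrong. They are not. A discharge-censored Cox model gives a valid cause-specific hazard ratio for death during the stay; the fault would lie in reading it as the effect on ICU or hospital mortality risk. Nor does the protocol say that one minus Kaplan-Meier will be reported as the mortality figure. It says that curves are displayed, and that categorical data are summarised as counts and percentages.

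A reader might also infer that the earlier trial's table proves the distortion. It does not. The hazard ratio of 1.32 has a 95% interval of 0.79 to 2.20, which contains 1.05. It comes from a subgroup that this trial does not enrol, and the difference in stay there has P = .26. In the severe subgroup, which this trial does enrol, the ICU hazard ratio and risk ratio are both 0.70, and the hospital hazard ratio is 0.56 against 0.54 implied. That trial's censoring rule is not given. The table is suggestive only.

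Finally, censoring rules are commonly SAP content, and the SAP prevails where the two differ. That permits a correction but does not make one. The protocol has not left the method open: it names one for these two outcomes, and the method fits them badly.

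**Conclusion.** The point holds as a should-fix on two secondary outcomes. The protocol assigns a fixed-horizon survival analysis to outcomes that have no stated horizon and that live discharge precludes.

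If discharge is censored, the Kaplan-Meier curves substantially overstate ICU and hospital mortality whether or not stays differ between arms. The hazard ratio departs from the effect on mortality risk only to the extent that discharge rates differ: about 1.37 in the 12.3 against 9.0 day illustration, and little when discharge rates are equal. These sizes rest on constant hazards, on medians and death fractions borrowed from the earlier trial, and on the censoring reading.

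A reader might extend the concern to the trial's main mortality result. The documents do not support that: the primary outcome, 90-day and 1-year mortality, the sample size and the interim boundary are unaffected.

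**What to change.** Limit the instruction to analyse as the primary outcome to 90-day and 1-year mortality. For ICU and hospital mortality, state a horizon (day 90, for example) and the handling of live discharge, and choose one of:

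- a binary analysis, with risk difference and risk ratio and their 95% confidence intervals;
- cumulative incidence to that horizon, with live discharge as the competing event.

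If a discharge-censored hazard ratio is kept, label it cause-specific and show the hazard ratio for live discharge beside it.

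The cost is a few lines of protocol or SAP text and slightly different code. No new data are needed. The downside is less uniform reporting across the mortality outcomes.
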